### 1.1. Objective

The aim of this study is to investigate the effect of hospitalisation due to acute illness on muscle mass characteristics, assessed in older adults through ultrasound. The primary endpoint is the change of characteristics of muscle mass in function of time since admission. The secondary endpoint of the study is to identify health related parameters associated with the development of acute sarcopenia. Relevant determinants of the evolution of muscle

mass and muscle strength since admission (reason of hospitalisation, comorbidities and laboratory data) will therefore also be investigated.

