## **1.2. Hypothesis**

Hospitalisation and acute illnesses will negatively affect both muscle mass and muscle function and will hereby contribute to the development of acute sarcopenia. We hypothesize that hospitalisation due to an elevated degree of inflammation will lead to more severe decrease of muscle mass and muscle function than hospitalisation due to non-inflammatory reasons. Furthermore, certain pre-existing conditions are supposed to increase the risk of acute sarcopenia.

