### **2.2. Subjects**

#### **2.2.1. Inclusion criteria**

Patients admitted between the 1st of November 2018 until the 31th of October 2019 will be eligible for inclusion. Included wards for admission are: internal medicine, acute geriatrics, orthogeriatrics and rehabilitation. Age limit will be set on 65 years and older.

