### 2.3.2. Muscle mass

In order to obtain reliable and consistent measurements, all ultrasonography will be done by an ultrasonographist that is trained to perform the measurements proposed. For the measurements, a linear probe of 5 cm width will be used. Frequency of the beam will be set on 12 MHz.

Patients should not have had any physical exercise in the 30 minutes before the measurement. Muscles should be completely relaxed and patients should be placed in the supine position, with hips in neutral position and knees fully extended. The dominant leg will be taken for the measurements. To calculate the relative muscle thickness values, the total length of muscle will be noted.

Ultrasonographic data of the four bellies of the quadriceps muscle (rectus femoris, vastus lateralis, vastus medialis, vastus intermedius) will be taken. Measuring points will be specified according to the propositions of the SARCUS-working group [19]. Muscle thickness, fascicle length, pennation angle, muscle cross-sectional area and echo-intensity of all muscles listed will be taken.

The first measurement will be taken as early as possible within 48 hours after admission at the latest. Follow-up measurements will be taken according to the type of ward the patient is admitted to. For patients that are expected to be hospitalized for a limited time (<5 days), the follow-up measurement will be done 3 days after initial measurement. For patients that are expected to be hospitalized for a longer time (>7 days), measurements will be repeated 7

days after initial measurement, to be repeated after another 7 days as long as the patient is hospitalized.

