### **2.3.3. Muscle strength and function**

Muscle strength will be measured through hand grip strength using a Jamar dynamometer, using the Southampton protocol [23]. The first measurement will be taken as early as possible within 48 hours after admission at the latest. Follow-up measurements will be taken according to the type of ward the patient is admitted to. For patients that are expected to be hospitalized for a limited time (<5 days), the follow-up measurement will be done 3 days after initial measurement. For patients that are expected to be hospitalized for a longer time (>7 days), measurements will be repeated 7 days after initial measurement, to be repeated after another 7 days as long as the patient is hospitalized. Measurement will be done directly after the ultrasonographic assessment. If feasible, muscle function will be measured through gait speed, using the 4-meter walking test at usual gait speed [24]. In case of those bedridden, gait speed will not be measured.

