## **2.4. Statistical analysis**

Databases will be kept up in a Microsoft Access database.

Statistical analysis will be done by using SPSS Statistics version 24. Descriptive analyses will be used for determining the clinical and demographic characteristics. A Kolmogorov-Smirnov test will be used to verify the normal distribution of the different variables. Further statistical analyses will be performed by Chi Square test, Fisher exact, Mann-Whitney U test or Fisher exact test, depending on the distribution and the nature of the variables analysed. P-values of  $\leq 0.05$  will be considered statistically significant.

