### 3. Discussion

This protocol has been designed to check whether acute illnesses or stressors followed by hospitalisation will promote the development of acute sarcopenia. This is a study protocol, and at this point no data are already available.

Although there are very few studies about the existence of acute sarcopenia, we hypothesize a relation between acute illnesses and acute sarcopenia [8]. We also hope to foresee health related parameters playing a crucial role in the accelerated development of sarcopenia, such as poor nutritional status before hospitalisation, acute inflammation and having a frail or sarcopenic status before the acute event. Certain pre-existing diseases are also believed to have an effect in worsening muscle parameters in acute illness or bedrest. It is important to identify risk factors for acute sarcopenia, so that strategies can be undertaken to prevent or at least delay the development of acute sarcopenia. Previous studies showed reduced intake of protein, reduced physical activity, inflammation, oxidative stress and low vitamin D as contributing factors to the development of (chronic) sarcopenia [9, 10, 30-32]. For acute sarcopenia, proposed risk factors include acute inflammation, reduced mobility, delirium, sleep disturbances, cognitive impairment, psychological stress and malnutrition [33-37].

A negative effect of bed rest on muscle mass has been already reported, and this effect is greater in older patients [7]. Also hypercortisolemia, as seen in acute stress and inflammatory conditions, was shown to decrease muscle mass in a study in which young adults were given hydrocortisone and bed rest [30]. Because of very fluctuating cortisol levels during the day, we chose not to measure cortisol in our study patients routinely.

Activity levels before the acute stressor occurrence, and then during hospitalisation could also be an influencing factor for acute sarcopenia. Determining activity prior to hospitalisation is however difficult. Possible tools are questionnaires like the Physical Activity Scale of the Elderly (PASE) [38] or the Seven Day Physical Activity Recall (SDPAR) [39], but those questionnaires are rather extensive and time-consuming. It could be a suggestion for further studies to examine the effect of activity pre-hospitalisation on acute sarcopenia. Activity levels during hospitalisation will be measured by use of pedometers in patients who are not bed- or chair bound.

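### Section 2.4 plans only unadjusted two-variable tests for the determinants of muscle decline, so a factor that travels with age or comorbidity can be reported as a determinant, or a real one missed

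*Combined protocol and SAP*

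**What the plan says.** Section 2.4 is the whole analysis plan. After descriptive statistics and a Kolmogorov-Smirnov check it lists chi-square, Fisher exact (twice) and Mann-Whitney tests, chosen by variable type and distribution ("Mann-Whitney U test or Fisher exact test, depending on the distribution and the nature of the variables analysed"), at p ≤ 0.05. No section mentions regression, a mixed model, stratification or a covariate list.

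The aims ask for more:

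- Section 1.1 sets the primary endpoint as "the change of characteristics of muscle mass in function of time since admission". It then states: "The secondary endpoint of the study is to identify health related parameters associated with the development of acute sarcopenia". It also promises to study determinants of how muscle mass and strength evolve, naming admission reason, comorbidities and laboratory data.
- Section 1.2: "We hypothesize that hospitalisation due to an elevated degree of inflammation will lead to more severe decrease of muscle mass and muscle function", compared with admissions for non-inflammatory reasons.
- Section 4 says the contribution of the measured parameters to the decline will be evaluated. Section 3 would direct screening and prevention by the result.

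On case mix, section 3 says that bed rest costs older patients more muscle, and adds: "Certain pre-existing diseases are also believed to have an effect in worsening muscle parameters in acute illness or bedrest". Section 2.2.1 says: "Included wards for admission are: internal medicine, acute geriatrics, orthogeriatrics and rehabilitation". The Abstract mentions only acute geriatric wards.

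On timing, section 2.3.2 says: "Follow-up measurements will be taken according to the type of ward the patient is admitted to". For short expected stays, section 2.3.3 says "the follow-up measurement will be done 3 days after initial measurement". For longer expected stays, measurement is weekly until discharge.

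**The concern.** A two-variable test compares patients with and without a factor as they come. If those with the factor are also older or sicker, and older or sicker patients lose more muscle, the test attributes that loss to the factor. If they are younger or healthier, a real effect can be masked. The test cannot separate a factor that only marks case mix from one that goes with faster loss in otherwise similar patients. A larger cohort does not help, because the spurious difference stays the same while the standard error shrinks.

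At stake are the secondary endpoint, the inflammation hypothesis, and the screening and prevention advice that section 3 wants to build on them. Age, sex and CIRS-G (section 2.3.1) and MNA-SF (section 2.3.5) are all collected, but section 2.4 gives them no adjusting role.

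**Working it through.** **What the documents settle.** The plan gives no sample size, standard deviation, loss rate or ward mix, so there is no figure to reproduce. Setting sections 1.1, 1.2 and 4 beside section 2.4 shows the gap directly: determinants and contributions are sought, and only unadjusted tests are named.

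**Illustration of case mix (all inputs assumed).** Four equal wards, everyone measured at day 7, SD of change 5%. Loss rises by 0.1, 0.2 or 0.3 SD per ward step, and the binary factor has no effect of its own. N is 200 or 400, tested two-sided at 5%.

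With factor prevalence 35/45/55/65% over wards coded 0 to 3, the mean ward code is:

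- with the factor: (0.45×1 + 0.55×2 + 0.65×3)/2.00 = 1.75
- without it: (0.55×1 + 0.45×2 + 0.35×3)/2.00 = 1.25

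The gap of 0.5 steps gives a spurious difference of 0.05, 0.10 or 0.15 SD.

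Hand check at 0.3 SD and N = 400 (200 per group): the ward code has variance 1.25, so the total SD is √(1 + 0.3²×1.25) = 1.055. The shift in z is (0.15/1.055)×√(200/2) = 1.42. P(Z > 1.96 − 1.42) is about 0.29. Simulation agrees:

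| Ward step | Aligned ordering, N = 200 | Aligned ordering, N = 400 |
|---|---|---|
| 0.1 SD | 6.0% | 7.1% |
| 0.2 SD | 11.8% | 14.8% |
| 0.3 SD | 17.2% | 28.8% |

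These are worst-case orderings, in which prevalence and loss rise together. Exactly opposite orderings give the same rates. Over all 24 ways of assigning the four prevalences to wards, the median rate was about 5% to 10%. With prevalence 45/48/52/55% the rate was 5% to 8%, and with even prevalence 5%. Adjusting for ward-by-time brought it to about 5% (4.6% to 5.5%).

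**A two-level confounder (an age or comorbidity group).** Assume it shifts change by 0.3 to 0.8 SD and the factor is split 60/40 across its levels. Unadjusted false positives were 7% to 19% at N = 200 and 10% to 31% at N = 400. With no imbalance they were 4% to 5%. Adjusted rates at these sizes were 4% to 6%. The result follows the inputs, which the documents do not give.

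**A real effect hidden.** With a true effect of 0.4 SD and the factor commonest where loss is least (again the extreme ordering), power was 37% to 92% unadjusted and 77% to 98% adjusted.

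**Follow-up length (conditional).** Assume last scans at 7/14/21 days in 45/35/20% of patients with the factor and 70/22/8% of those without. Mean follow-up is then 0.45×7 + 0.35×14 + 0.20×21 = 12.25 days against 0.70×7 + 0.22×14 + 0.08×21 = 9.66 days. At a common loss of 0.5% per day, raw change to the last scan differs by 2.59×0.5 = 1.3 percentage points although the daily rates are equal. Comparing day 7 only gave false positives of 4% to 6%.

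**Form of the model.** In a fitted mixed model (step 0.2 SD, prevalence 35–65%), ward as a main effect only left the factor-by-time estimate equal to the raw difference in change, with false positives of 10.3% and 15.4% at N = 200 and 400. Ward-by-time terms gave 4.5% and 5.9%. A single linear slope gave 12% to 63% when loss decelerated and follow-up was unequal; categorical time gave 4% to 6%.

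**The case against.** The strongest reply is that the secondary endpoint is worded as association, and an unadjusted association can serve screening. That stands, and is a reason to keep the existing tests as description. It does not cover the determinants in section 1.1, the comparative hypothesis in section 1.2 or the contribution to decline in section 4.

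Comorbidity is also a candidate determinant, and the section 3 sentence about pre-existing diseases is the study's own expectation, not evidence. That is fair. But a variable expected to drive loss is one to hold constant when another factor is tested.

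Three stronger readings are tempting and are not supported:

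- *That pooling four ward types confounds the results.* The Abstract restricts to acute geriatric wards, no section says that loss differs by ward, and section 2.2.1 does not say how wards are handled in analysis. Ward is a confounder only if section 2.2.1 governs.
- *That a false-positive rate near 28% is to be expected.* It belongs to the least favourable ordering at the largest assumed effect and sample size.
- *That unequal follow-up biases the inflammation comparison.* This needs raw change to the last scan as the outcome, which the plan does not state. Section 1.1 equally allows comparison at like days, and nothing in the documents links inflammation to length of stay.

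Adjustment can also go too far. Ward may stand for admission reason, so ward terms could remove part of the contrast in section 1.2.

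**Conclusion.** The point holds as a gap between aims and methods: no adjusted analysis is planned, while the protocol names age and pre-existing disease as influences on muscle loss. Whether any particular result would mislead, in which direction and by how much, cannot be derived from the documents. It depends on how unevenly the factor is spread over case mix and on how strongly case mix drives loss. With no imbalance there is no inflation. In the four-ward illustration the rate is typically 5% to 10% and at most about 28%. The age and comorbidity part does not depend on how change is defined. The ward part depends on which eligibility statement governs, and the follow-up part on an outcome definition that is not given. This is a cheap improvement that should be made, not a reason to discard the study.

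**What to change.** In section 2.4, keep the unadjusted tests as descriptive and make the determinant analysis adjusted:

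1. **Continuous measures** (ultrasound, grip, and gait speed where measured): a linear mixed model with scheduled day as categories, or flexible time, and a factor-by-time term. Adjust for a short pre-specified set (age, sex, CIRS-G) with covariate-by-time terms, adding MNA-SF if numbers allow. Account for centre. State the target as the difference in change at the same named day, and do not compare raw change to the last scan.
2. **Acute sarcopenia, yes or no:** logistic regression at a common day with the same covariates. The Abstract defines acute sarcopenia by meeting criteria, so the linear model alone would leave this endpoint unadjusted.
3. **Inflammation hypothesis:** test inflammatory against non-inflammatory admission reason, as section 1.2 frames it, with log CRP as a supporting analysis.
4. **Ward:** reconcile the Abstract with section 2.2.1, and report results with and without ward.
5. Do not adjust for a covariate that is itself the factor under test.

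The cost is a rewritten section 2.4 and modest analysis work on data already collected. The core set adds three covariate-by-time terms per follow-up day, four with MNA-SF, and three more in the analysis with four wards. The added terms cost some precision. As no sample size is stated, the covariate set should be kept short if few patients are enrolled.

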## **2.5. Ethics**

We will comply with both international and country specific guidelines concerning research ethics. We will also adhere to the World Medical Association Declaration of Helsinki. A written information flyer will be given to all patients and/or their family, and a written informed consent will be registered in the medical file. In patients with cognitive disorders, informed consent will be taken from the family or the main representative (proxy signature). The local

ethical committee agreement of all participating study sites will be obtained before the start of the study.

### 3. Discussion

This protocol has been designed to check whether acute illnesses or stressors followed by hospitalisation will promote the development of acute sarcopenia. This is a study protocol, and at this point no data are already available.

Although there are very few studies about the existence of acute sarcopenia, we hypothesize a relation between acute illnesses and acute sarcopenia [8]. We also hope to foresee health related parameters playing a crucial role in the accelerated development of sarcopenia, such as poor nutritional status before hospitalisation, acute inflammation and having a frail or sarcopenic status before the acute event. Certain pre-existing diseases are also believed to have an effect in worsening muscle parameters in acute illness or bedrest. It is important to identify risk factors for acute sarcopenia, so that strategies can be undertaken to prevent or at least delay the development of acute sarcopenia. Previous studies showed reduced intake of protein, reduced physical activity, inflammation, oxidative stress and low vitamin D as contributing factors to the development of (chronic) sarcopenia [9, 10, 30-32]. For acute sarcopenia, proposed risk factors include acute inflammation, reduced mobility, delirium, sleep disturbances, cognitive impairment, psychological stress and malnutrition [33-37].

A negative effect of bed rest on muscle mass has been already reported, and this effect is greater in older patients [7]. Also hypercortisolemia, as seen in acute stress and inflammatory conditions, was shown to decrease muscle mass in a study in which young adults were given hydrocortisone and bed rest [30]. Because of very fluctuating cortisol levels during the day, we chose not to measure cortisol in our study patients routinely.

Activity levels before the acute stressor occurrence, and then during hospitalisation could also be an influencing factor for acute sarcopenia. Determining activity prior to hospitalisation is however difficult. Possible tools are questionnaires like the Physical Activity Scale of the Elderly (PASE) [38] or the Seven Day Physical Activity Recall (SDPAR) [39], but those questionnaires are rather extensive and time-consuming. It could be a suggestion for further studies to examine the effect of activity pre-hospitalisation on acute sarcopenia. Activity levels during hospitalisation will be measured by use of pedometers in patients who are not bed- or chair bound.

Nutritional status at admission will be noted via the MNA-SF questionnaire [25], complementary with selected laboratory values. Although aware that malnutrition or starvation during hospitalisation will probably play an important role in development of acute sarcopenia, we chose not to register the actual nutritional intake in hospital with food record charts, because such measurements are very much observer-dependent and hereby very prone to inaccuracy.

The most important advantage of our study is that muscle mass will be measured via ultrasound, which is a relatively new way of sarcopenia screening and assessment [18, 40]. It is much more available than bio-impedance analysis or DEXA, and with less side effects than CT. It can easily be performed on a daily basis in all patients at risk for sarcopenia.

Other strengths of this study are the size of the study population (due to the multicenter setting), the comprehensiveness of assessment and the frequent, regular follow-up measurements.

There are some limitations to the study. Food intake during hospitalization will not be measured. Although nutritional intake is an important factor in retaining muscle mass, it is very difficult to correctly assess caloric and protein intake in acute patients. Also, no good measure for physical activation prior to hospitalisation is included in this research, as making a correct assessment of total exercise time and level through post-hoc recollection is often biased.

Once risk factors of acute sarcopenia are identified, we suggest to screen in those individuals in the first instance, and to pay attention to available prevention and treatment strategies. First of these strategies are physical activity interventions, with early mobilisation and intensive physical activity during hospitalisation [41]. Especially resistance exercise training and moderate aerobic exercises have been shown beneficial in improving muscle mass and function [42]. Furthermore, some nutritional interventions like protein supplementation are believed to help to prevent loss of muscle mass [43]. Especially leucine amino acid intake would be important [44]. Other interventions are still more controversial. Neuromuscular electrical stimulation (NMES) is described to prevent reductions in muscle fibre cross-sectional area [45]. This technique is however not very useful for prevention of total body skeletal muscle loss. Pharmacological interventions have been suggested for treatment of established sarcopenia, like Calorie Restriction Mimetics (CRM) and Exercise Mimetics (EM) under the form of phytochemicals [46]. Also recombinant growth hormone, testosterone supplementation, dihydroepiandrosterone and myostatine have been trialled with variable results [47-49][50]. More studies are needed to establish better pharmacological therapies to prevent or treat (acute) sarcopenia.

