## Abstract

Sarcopenia is a geriatric syndrome defined as progressive and generalized age-related muscle loss with decline in muscle mass and muscle function (either strength or performance). It is closely related to adverse outcomes such as frailty, reduced quality of life, increased risk of falling, more frequent hospitalisations and higher mortality. Acute sarcopenia is the decline of muscle mass and function following acute disease or hospitalisation, sufficiently to meet the criteria of sarcopenia.

Objectives: To assess the effect of hospitalisation and acute illness on muscle mass and function, and to assess which other factors contribute to the development of acute sarcopenia.

Study design and main outcome measures: This study is a prospective multicenter observational study. Patients admitted to acute geriatric wards of different European centers and hospitalised for at least 5 days will be included. Measurements of muscle mass will be performed via ultrasound. Measurements of muscle function will be done by hand grip strength using Jamar dynamometer and by gait speed using the 4-meter walking test, when feasible. Other parameters will be measured via file study, laboratory investigations or validated questionnaires. Activity levels during hospitalisation will be measured through pedometers.

Anticipated results: Decline of muscle mass and muscle characteristics secondary to hospitalisation. We also expect an association with reasons of hospitalisation, pre-existing conditions, laboratory results and nutritional status prior to hospitalisation on the decline in muscle parameters.

Conclusions: This study seeks to gain knowledge of the development of acute sarcopenia and its contributing factors.

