### **2.3.4. In-hospital activity**

Registration of activity level during hospitalisation will be performed by means of pedometers in those centers that have access to these devices. Both amount of steps and step length will be noted, and total walked distance per day can hereby be calculated.

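### Pedometers are withheld from bed- or chair-bound patients and no other in-hospital activity value is planned for them, so immobile and mobile patients cannot be compared on activity

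*Combined protocol and SAP*

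**What the plan says.** Three places in the protocol describe who has activity measured, and they differ.

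- **Abstract:** "Activity levels during hospitalisation will be measured through pedometers". No restriction is given.
- **Section 2.3.4:** the restriction is by centre only, to "in those centers that have access to these devices".
- **Section 3 (Discussion):** a patient-level restriction is added: "Activity levels during hospitalisation will be measured by use of pedometers in patients who are not bed- or chair bound".

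The activity variable is defined in section 2.3.4: "Both amount of steps and step length will be noted, and total walked distance per day can hereby be calculated". No other measure of in-hospital activity or bed rest is described.

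Bedridden patients are part of the study. Section 2.3.1 explains how to weigh them, and section 2.3.3 says their gait speed is not taken.

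The Discussion gives the reason for measuring activity: "For acute sarcopenia, proposed risk factors include acute inflammation, reduced mobility, delirium, sleep disturbances, cognitive impairment, psychological stress and malnutrition". On immobility itself it adds: "A negative effect of bed rest on muscle mass has been already reported, and this effect is greater in older patients".

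Section 2.4 names chi-square, Fisher exact and Mann-Whitney tests. It has no regression model and no rule for missing values.

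**The concern.** The device is withheld according to the exposure it is meant to measure. Patients at the immobile end of the range have no step count, and nothing in the plan gives them a zero or a category of their own. They also lack gait speed. A blank activity field would look the same for a bedridden patient, a patient at a centre without devices and a patient whose device was lost.

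The plan's own rationale expects muscle loss with bed rest. Its activity data, however, can only compare patients who walk more with patients who walk less. If much of the effect lies between immobile and mobile patients, the study could report little or no association with activity although immobility matters. The limitations paragraph in section 3 mentions food intake and pre-hospital activity but not this gap.

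**Working it through.** **The plan's own figures.** There are none to reproduce: no sample size, power, effect size, standard deviation or immobile share is given. Everything below is illustration on assumed inputs.

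**Assumed inputs.** Latent activity X is standard normal. Its correlation with muscle change is 0.30. The lowest share q of X is bed- or chair-bound, with q = 20%, 30% or 40%. There are N = 150 patients at pedometer centres, and alpha is two-sided 0.05 (section 2.4 gives p ≤ 0.05 without sidedness).

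**Step 1: rank correlation, by simulation.**

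| Immobile share | Immobile ranked lowest, n = 150 | Walkers only | n of walkers |
|---|---|---|---|
| 20% | 0.28 | 0.22 | 120 |
| 30% | 0.28 | 0.20 | 105 |
| 40% | 0.27 | 0.19 | 90 |

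**Step 2: power by Fisher's z.** Power ≈ Φ(atanh(r) × √(n − 3) − 1.96).

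- 20%, all patients: atanh(0.28) = 0.288; × √147 = 3.49; minus 1.96 = 1.53; power 94%.
- 20%, walkers: atanh(0.22) = 0.224; × √117 = 2.42; minus 1.96 = 0.46; power 68%.
- 30%, walkers: atanh(0.20) = 0.203; × √102 = 2.05; minus 1.96 = 0.09; power about 53% (about 55% with the unrounded correlation). With all patients it is 93-94%.
- 40%, all patients: atanh(0.27) = 0.277; × √147 = 3.36; minus 1.96 = 1.40; power 92%.
- 40%, walkers: atanh(0.19) = 0.192; × √87 = 1.79; minus 1.96 = −0.17; power 43%.

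**Step 3: a group contrast, closer to the tests in section 2.4.** Split activity at its median and compare mean muscle change. If every patient had a true activity value, the difference would be 0.48 SD. In walkers only it is 0.37, 0.34 and 0.31 SD for q = 20%, 30% and 40%, that is 77%, 71% and 64% of the full contrast. With a hypothetical 200 patients before exclusion, power falls from about 92% to 66%, 54% and 41%.

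**Step 4: does a regression slope suffer in the same way?** It depends on the shape of the effect.

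- *Linear effect:* the slope in walkers stays at 0.30 for every q. Precision is lost, but there is no bias.
- *Immobile patients lose an extra 0.5 SD:* the slope falls from 0.44, 0.48 and 0.49 (q = 20%, 30%, 40%) to 0.30.
- *Only immobile patients lose muscle:* the estimated activity effect in walkers is about zero.

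**Step 5: would other coefficients in an adjusted model be biased?** Take a true activity effect of 0.30, a CRP effect of −0.20 and an activity-CRP correlation of −0.4, and drop the lowest 20-40%. The complete-case CRP coefficient is −0.199, −0.199 and −0.198, and activity stays at 0.30. Selection on a covariate that is in a correctly specified model does not bias that model.

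**Step 6: does a bare zero repair a regression?** No. Giving all immobile patients one floor value, placed at the cut-off, moves the activity coefficient to 0.34, 0.36 and 0.39 and the CRP coefficient to −0.21, −0.22 and −0.23. Adding an immobile indicator keeps the activity slope at about 0.29-0.30.

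**The case against.** The strongest case on the other side has four parts.

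- **Low stakes.** Activity is not among the determinants in section 1.1 or the hypotheses in section 1.2, and pedometers are already optional by centre. Bed-bound patients still have ultrasound and grip strength. This stands, and it sets the severity.
- **A valid result in walkers.** A smaller correlation among walkers correctly describes walkers, and a linear slope is not biased. This also stands. The loss is the missing immobile-versus-mobile contrast, plus weaker group and rank tests; it is not a general bias in every activity estimate.
- **Inferred from silence.** Withholding a device is not a coding rule, and staff must know who is bed- or chair-bound in order to withhold it. That is so, but the plan does not say that this status is stored or analysed. The point shows that the repair is cheap; it does not show that the repair is planned.
- **Assumed figures.** The correlation, immobile share and sample size come from outside the plan, and rank correlation is not among the tests in section 2.4. The figures also take immobile patients to be exactly the lowest part of one activity scale. All of this is correct, so the figures show direction and plausible size only.

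A reader might also infer that deleting bed-bound patients would bias the CRP and nutrition results. The documents do not support this: section 2.4 plans no adjusted model, and under a linear model the complete-case CRP coefficient is unchanged (step 5).

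**Conclusion.** The point holds as a gap in an exploratory determinant. Followed as written, the Discussion's rule removes the immobile end of the activity range, and nothing else in the plan restores it. The immobile-versus-mobile contrast cannot be estimated from the planned activity data.

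Group and rank comparisons in walkers are attenuated under the scenarios tried. With the assumed correlation of 0.30, 20-40% immobile and 150 patients, power drops by roughly 26 to 49 percentage points (94 − 68 = 26; 92 − 43 = 49). A linear slope among walkers keeps its value if the effect is linear, and understates the overall association if immobile patients lose disproportionately more.

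It would go too far to conclude that activity effects are biased toward zero whatever the method, or that the primary endpoint is affected. Severity is low.

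**What to change.** 1. In all centres, record mobility status (bed-bound, chair-bound, walking) from the ward file for each measurement interval. Set up the field before data collection, since past days may be hard to reconstruct.
2. Pre-specify immobile patients as the lowest activity category, so that immobility can be analysed where there are no pedometers.
3. In pedometer centres, rank immobile patients lowest in group and rank tests, with a zero flagged as assigned rather than measured. In any regression, use an immobile indicator and not a bare zero.
4. Reconcile the Abstract, section 2.3.4 and section 3 on who is measured, and let the database distinguish immobile, no device at the centre, and device data lost or refused.

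The cost is one extra recorded field and one coding rule, with no further devices. The category is coarse for chair-bound patients who take some steps, and it does not resolve differences within the immobile group.
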